#### **3.0 DESIGN AND METHODS**

#### 3.1 Study Design:

The study design is an Individual Randomized Parallel-Group Trial study with both an intervention group and a control group in Wakiso district, Central Uganda. All women with Metabolic Syndrome identified in our baseline study will be randomized to either intervention and control groups. The intervention will be administered in 5 groups of 12 participants.

#### 3.2 Study Arms:

The study will employ two study arms; an intervention group and a control group.

#### 3.3 The interventions

#### Intervention: Nutrition/dietary education and motivational interviewing

The nutritional promotion intervention will consist of two components: group motivational interviewing and group nutrition education sessions. These will be provided by a team consisting of the principle investigator, nutritionists, health workers (nurses/clinical officers) and community psychologist.

#### **Dosage of the intervention**

The nutrition intervention will consist of one hour of weekly group seminar sessions for 12 sessions and one hour of monthly individual motivational interviewing sessions for 3 sessions undertaken for 3 months. The choice of the group sessions in our study was determined to be sufficient intervention duration based on studies with similar methodologies [22]. In our study, group sessions will be held in a safe and convenient community location such as a community center, health facility or place for religious gathering with a hall for community activities.

For group nutrition education, written and oral instruction will be used including lectures, power point and poster presentations. Individual counselling will employ motivational counselling techniques. The intervention group will have 60 participants. This will form about 12 participants per group, with a total of 5 groups. Each group will be under the direct supervision of one trained nutritionist. The nutritionist will be located in 5 enumeration areas and will provide the intervention package to the participants as stated above. The nutritionists will undergo 18 hours of training on the delivery of the curriculum designed for the study.

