#### Package of the group motivation interviewing sessions

3 sessions of group motivation interviewing (MI) will be held monthly over 3 months in groups of approximately 12 participants covering various topics, including goal setting, factors that motivate lifestyle and behavioural change, relapse and its management, coping strategies and support, eating habits at various settings. Discussions will be held on relevant topics using MI techniques.

**Comparison:** In the comparison group, participants with MetS will be subjected to only usual standard of care with no specific individualized interventions. This will include referral of the participants to the usual health care facilities for management of their conditions as per the existing routine health facilities protocols. This is for purposes of controlling for possible changes in outcome variable due to other influences or behaviours.

Effort will be undertaken to reduce non-adherence in intervention group through evaluating questionnaires and meeting attendance, use of paper and phone reminders, provision of information about study objectives and planned meeting schedules, and reinforcement of the need for compliance during follow up meetings.

 Table 2: Summary table for the intervention and non-intervention arms

No.	Intervention arm	Control arm
1.	Participants =60 women of reproductive age with MetS divided into 6 groups at baseline	Participants =60 women of reproductive age with MetS (no groups) at base line
2.	Intervention and duration: One hour of weekly group nutrition education seminar sessions offered for 12 sessions in 3 months and One hour of monthly group motivational interviewing sessions offered for 3 sessions undertaken for 3 months.	Duration of follow up: Usual standard of care in nutrition education varies depending on either inpatient or outpatient setting
	Behavioral change for dietary intake and physical activity enhanced by, motivation interviewing	Usual standard of care in nutrition education and counselling. There is limited or no focus on Motivational Interviewing for behavioural cchange
	Delivered by: Nutritionists and health workers using a tailor made curricular guide and materials for MetS	Delivered by: Nutritionists and health workers using nutrition guides and materials for management of malnutrition (under and over nutrition)

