#### 3.5 Recruitment and enrollment of participants

We will use the database of a baseline study conducted to determine the prevalence of Metabolic Syndrome in Wakiso district (Manuscript under peer review) as our source of participants. Those participants who were diagnosed with MetS will be recruited into the study.

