#### **Randomization: Sequence generation**

The randomization procedure will be automatically performed by a biostatistician to minimize the differences between the two groups for all stratifying variables. Using a computer random number generator a randomisation list of permuted blocks of size 8 with an allocation ratio of 1:1 will be generated. Then the participants will be randomly allocated to either the intervention arm (60) or the control group (60) and followed up for 3 months.

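### Sessions are planned around five local groups, but allocation runs from one list in which area is not a named factor; running the blocks within delivery area is a cheap improvement

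*Protocol*

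**What the plan says.** **Delivery.** Section 3.1 states: "The intervention will be administered in 5 groups of 12 participants". Section 3.3, under Dosage of the intervention, is slightly looser: "This will form about 12 participants per group, with a total of 5 groups". It goes on: "Each group will be under the direct supervision of one trained nutritionist", and then: "The nutritionist will be located in 5 enumeration areas and will provide the intervention package to the participants as stated above". On venue it says that "group sessions will be held in a safe and convenient community location such as a community center, health facility or place for religious gathering". Section 3.8 staffs the sessions in fives: five nutrition trainees, five sports scientists and five health workers for motivational interviewing. Table 2 departs from this and describes the intervention arm as "60 women of reproductive age with MetS divided into 6 groups at baseline".

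**Source of participants.** Section 3.5: "We will use the database of a baseline study conducted to determine the prevalence of Metabolic Syndrome in Wakiso district". Section 3.1 says that every woman found to have metabolic syndrome in that study is to be randomized.

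**Allocation.** Section 3.7, Sequence generation: "Using a computer random number generator a randomisation list of permuted blocks of size 8 with an allocation ratio of 1:1 will be generated". The same section mentions stratifying variables without naming any. Under Allocation Concealment it mentions a minimization algorithm, again with no factors named. It then describes envelopes numbered 1 to 120, handed out in sequence to one list of names that has itself been put in random order. Consent follows randomization.

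The protocol does not say how the 60 intervention women are placed into session groups, whether a woman attends in her own area, how many eligible women each area holds, or whether all 120 come from the five areas.

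**The concern.** The delivery plan is tied to place and the allocation procedure, as described, is not. If women attend near home, the number of intervention women in each area depends on chance and on how many eligible women that area supplied. Some nutritionists could then lead noticeably smaller or larger groups than planned, and an area could contribute more women to one arm than to the other.

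Balance on area is a usual target for stratification when delivery is local. Diet, access to care and the provider may all vary by place, and removing chance imbalance on such a factor costs little. The block size already chosen would serve for this, but only if a separate sequence is run for each area.

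**Working it through.** **Inputs from the protocol.** 120 women; blocks of 8 at 1:1; 60 per arm; five groups of about 12; five enumeration areas.

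**Assumptions, not in the protocol.** Session groups follow area of residence. Area plays no part in allocation. In the base case each area supplies 120/5 = 24 women.

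**1. The plan's own figure.** 120/8 = 15 blocks, each giving 4 intervention women, so 15 × 4 = 60. Then 60/5 = 12. As a head count, five groups of 12 reproduces. Table 2's six groups would give 60/6 = 10.

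**2. Spread within one area.** Because the names are in random order, the intervention count in an area of 24 is hypergeometric, and blocking on the list does not change this.

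- Mean = 24 × 60/120 = 12.
- SD = √(24 × 0.5 × 0.5 × 96/119) = √4.84 = 2.20.
- The control count is 24 minus the intervention count, so the difference between arms within an area has SD 2 × 2.20 = 4.4.
- P(x) = C(24, x) × C(96, 60 − x) / C(120, 60). Summed over x = 10 to 14, this is 0.746, so a given area falls in that range about 75% of the time.

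**3. All five areas together.**

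- P(all exactly 12) = C(24, 12)⁵ / C(120, 60) = 0.0015. This is shown only for completeness, since the protocol says about 12.
- In 20,000 simulated lists (15 blocks of 8, names in random order), the mean smallest and largest groups were 9.1 and 14.8. The 5th percentile of the smallest was 7 and the 95th percentile of the largest was 17.
- All five lay within 10 to 14 in about 28% of lists, so at least one fell outside in about 72%.

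**4. Range over unequal area sizes (assumed).**

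| Women per area | Median smallest | Median largest | All five within 10–14 |
|---|---|---|---|
| 24, 24, 24, 24, 24 | 9 | 15 | about 28% |
| 30, 27, 24, 21, 18 | 8 | 16 | about 8% |
| 40, 30, 20, 18, 12 | 6 | 20 | about 0.02% |

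Much of the spread in the last two rows comes from the area sizes themselves. Stratifying would not remove that part.

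**5. With blocks of 8 run within area.** An area of 24 has 24/8 = 3 complete blocks, giving 3 × 4 = 12 intervention and 12 control women on the list. For other sizes each complete block is balanced, and the last, incomplete block can put at most 4 women in one arm before the other starts to fill. The arms within an area therefore differ by at most 4, against an SD of 4.4 for that difference under the single list with 24 per area.

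**The case against.** The strongest reply is that the protocol never says groups follow residence. Sessions are at a convenient community venue, section 3.8 puts them at weekends, and all allocations are made in one step. Sixty known women can then be divided into five groups of 12 whatever their area. That stands. The figures above are conditional, and a reader who inferred that the allocation will fail to produce the planned groups would go beyond the text.

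Three further points also stand.

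- The target is about 12, so the very small chance of exactly 12 in every area is not a test the plan must pass.
- Area is not ruled out as a factor, because the stratifying variables and minimization factors are unnamed. However, the mechanism actually described, one sequence matched to one randomly ordered list, does not stratify on anything. If area was intended, the text needs to say so.
- A reader might infer that area or provider is confounded with arm. It is not: with areas of 40, 30, 20, 20 and 10, both arms average 20, 15, 10, 10 and 5. What remains is chance imbalance. Providers exist only in the intervention arm by design, and stratifying would not change that.

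A reader might also infer that distance will reduce attendance. The protocol gives no figure on travel or attendance by area, so that is plausible but not shown.

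**Conclusion.** The point holds as a recommended improvement, not as a demonstrated failure. Delivery is organised around five local groups, the described allocation does not use area, and no rule connects the two. If groups follow residence and each area supplied 24 women, the per-area intervention count has SD 2.2, the expected extremes are about 9 and 15, and all five areas fall within 10 to 14 about 28% of the time. With less equal areas the spread is wider. Both the residence rule and the area counts are assumptions, since the protocol gives neither.

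The consequence is uneven group size and chance imbalance of area between arms. Random allocation still leaves the arm comparison unbiased. Separately, five groups in sections 3.1 and 3.3 and six in Table 2 contradict each other whatever view is taken of allocation.

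**What to change.** 1. Before allocation, assign every eligible woman to one of the five delivery areas, including women who live outside them. Do not restrict the frame: section 3.1 commits to randomizing all women with metabolic syndrome from the baseline study.
2. Run the 1:1 permuted blocks of 8 separately within each delivery area, name area as the stratifying variable, and bring the minimization wording into line with this.
3. State that a woman allocated to the intervention joins the session group of her delivery area.
4. Include delivery area as a covariate in the between-group models.
5. Reconcile five groups with the six in Table 2. If the number of delivery areas changes, the number of lists changes with it.

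**Cost.** Five short lists instead of one, drawn up before allocation, with block size and ratio unchanged. Incomplete final blocks may move the totals slightly from 60/60.

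**Limits.** Groups of exactly 12 are not guaranteed, because group size still depends on how many women each area supplies and on who consents after randomization. What the change secures is near 1:1 balance on the list within each area.

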#### Package of the group nutrition education sessions

The package will be guided by the curriculum and will mainly focus on the importance of health diet in MetS, healthy food choices, adequate daily distribution of meals, daily fat consumption targets, eating habits, serving sizes and portion sizes, goals for weight loss, techniques for diet compliance for weight loss, shopping tips for healthy food choices, food preparation and modification, meal planning, health eating (increasing intake of fruits, vegetables, fish and water and reducing consumption of sugar, fat, sodium, and fried foods) to reduce the components of metabolic syndrome and using photo books with examples of health meals. Additionally, participants will be encouraged to do moderate-intensity physical activity like brisk walking, climbing stairs and housework for at least 45 minutes.

#### Package of the group physical activity intervention sessions

Group physical activity sessions will cover a range of topics, including the different physical activity types, the importance of physical activity, and ways to incorporate physical activity into daily life, the WHO recommendations for physical activity and simple physical activity routines, the levels of physical activity and strategies to increase it, the risks associated with physical activity, exercise safety, and injury prevention, overcoming common barriers to exercise, staying motivated, nutrition for physical activity, and monitoring progress with exercise logs. Participants will receive encouragement to perform a minimum of 150 minutes of moderate-intensity or 75 minutes of vigorous-intensity aerobic physical activity per week, which includes activities like running, climbing stairs, and participating in sports. Additionally, participants will be encouraged to actively participate in muscle-strengthening activities, such as going to the gym, lifting heavy objects, or practicing yoga, for a minimum of two days per week, at a moderate level of intensity. Participants will receive guidance to decrease sedentary behavior by substituting it with any level of physical activity. Participants will receive leaflets containing key messages for their reference.

#### Package of the group motivation interviewing sessions

3 sessions of group motivation interviewing (MI) will be held monthly over 3 months in groups of approximately 12 participants covering various topics, including goal setting, factors that motivate lifestyle and behavioural change, relapse and its management, coping strategies and support, eating habits at various settings. Discussions will be held on relevant topics using MI techniques.

**Comparison:** In the comparison group, participants with MetS will be subjected to only usual standard of care with no specific individualized interventions. This will include referral of the participants to the usual health care facilities for management of their conditions as per the existing routine health facilities protocols. This is for purposes of controlling for possible changes in outcome variable due to other influences or behaviours.

Effort will be undertaken to reduce non-adherence in intervention group through evaluating questionnaires and meeting attendance, use of paper and phone reminders, provision of information about study objectives and planned meeting schedules, and reinforcement of the need for compliance during follow up meetings.

 Table 2: Summary table for the intervention and non-intervention arms

No.	Intervention arm	Control arm
1.	Participants =60 women of reproductive age with MetS divided into 6 groups at baseline	Participants =60 women of reproductive age with MetS (no groups) at base line
2.	Intervention and duration: One hour of weekly group nutrition education seminar sessions offered for 12 sessions in 3 months and One hour of monthly group motivational interviewing sessions offered for 3 sessions undertaken for 3 months.	Duration of follow up: Usual standard of care in nutrition education varies depending on either inpatient or outpatient setting
	Behavioral change for dietary intake and physical activity enhanced by, motivation interviewing	Usual standard of care in nutrition education and counselling. There is limited or no focus on Motivational Interviewing for behavioural cchange
	Delivered by: Nutritionists and health workers using a tailor made curricular guide and materials for MetS	Delivered by: Nutritionists and health workers using nutrition guides and materials for management of malnutrition (under and over nutrition)
	Intervention topics and content : Focus on health dietary practices to manage MetS and prevent chronic non communicable diseases; over nutrition and associated risk of developing chronic non communicable diseases. Specifically: Types of nutrients and food sources: carbohydrates, protein, fats and cholesterol. Intake of sugar, salt, saturated and non-saturated fats and daily fat consumption targets Diary intake Fruit and vegetable intake Portion sizes and serving sizes Making health food choices Menu planning and food preparation Physical activity Goal setting Lifestyle modification	Usual standard of care in nutrition education target prevention and management of malnutrition
	Assessment of fidelity of implementation: supervision of trainers and frequent meetings by principle investigator with the trainers	None

#### **3.4 Study Participants:**

Female aged 15-49 years with Metabolic Syndrome in Wakiso district.

The intervention group participants will be women identified in Wakiso district during our baseline study. The intervention group will receive group nutritional education, group physical activity, and motivational interviewing. The control group also with Metabolic Syndrome identified in Wakiso district in the baseline study will receive usual standard of care.

**Inclusion Criteria:** Being a female aged 15-49 years in Wakiso district, Central Uganda with metabolic syndrome (defined by the 2009 Joint Interim Statement (JIS)), living in the community for at least one year, able to provide informed consent (oral or written), including consent for a follow-up interview 3 months after the start of the study. Participants under 18 years, should be able to provide assent and get informed consent from their parent /guardian or legal representative.

**Exclusion Criteria:** Females with chronic diseases such as liver, kidney, heart diseases or any diseases that could be worsened or affected by intervention sessions, participants on a prescribed diet plan, and those with the potential to undergo any surgical procedure during the intervention period.

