#### **OPERATIONAL DEFINITIONS**

**Cardiovascular diseases:** These diseases include coronary heart disease, cerebro-vascular disease, raised blood pressure, peripheral artery disease, rheumatic heart disease and congenital heart disease.

**Metabolic:** This refers to biochemical processes involved in the body's normal functioning **Metabolic Health:** This refers to an individual's possession of optimal levels of blood sugar, triglycerides, high-density lipoprotein (HDL) cholesterol, blood pressure, and waist circumference, without using medications

**Metabolic Syndrome:** Metabolic syndrome (MetS) is a cluster of risk factors for type 2 diabetes (T2DM) and cardiovascular disease (CVD). It is defined by five components [raised waist circumference (WC), raised triglycerides, reduced high density lipoprotein (HDL) Cholesterol, raised fasting glucose and raised blood pressure (BP)].

**Motivational interviewing:** "Motivational interviewing is a directive, client-centered counseling style for eliciting behavior change by helping clients to explore and resolve ambivalence"[1]

**Physical activity:** Is defined as "any bodily movement produced by skeletal muscles that results in caloric expenditure"[2].

**Prevalence of metabolic health:** This refers to the proportion of people who have optimal levels of all the risk factor variables without any medication.

**Reproductive age:** This refers to the female in the age group 15-49 years.

**Reproductive factors:** This refers to factors of reproductive history including early menarche, parity, miscarriages, and menopause.

**Risk factor:** This refers to an 'aspect of personal behavior or lifestyle, an environmental exposure, or a hereditary characteristic that is associated with an increase in the occurrence of a particular disease, injury, or other health condition'.

**Modifiable risk factor:** A behavioral risk factor that can be reduced or controlled by intervention, thereby reducing the probability of disease for instance obesity, dietary habits, psychosocial factors, alcohol abuse and cigarette smoking.

**Non-modifiable risk factor:** A risk factor that cannot be reduced or controlled by intervention for instance age, sex, race, genetics/family history

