#### 3.6 Outcomes of interest:

#### **Primary outcome**

The primary outcome will be the between–group change in MetS prevalence after 3 months from start of intervention.

The 2009 Joint Interim Statement (JIS) will be used to diagnose MetS, defined as the presence of  $\geq$  3 of the following 5 factors: increased WC (women:  $\geq$  80 cm), low HDL-C (women: <50 mg/dl (1.3 mmol/l) or treatment of low HDL-C), Hypertriglyceridemia  $\geq$ 150 mg/dl (1.7 mmol/l) or treatment, elevated BP (systolic BP  $\geq$  130 mmHg and/ or diastolic  $\geq$ 85

mmHg or treatment for hypertension) and elevated fasting blood sugar (FPG  $\geq$  100 mg/dl (5.6 mmol/l) or diabetes mellitus or treatment[3]

The European cutoffs for waist circumference will be used as recommended by WHO because of the unavailability of population/country specific WC cutoffs for sub-Saharan Africans [3] or Uganda.

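### Pregnancy is neither excluded nor recorded in a trial of women aged 15-49 whose outcomes include waist, weight, blood pressure, glucose and lipids; the likely result is modest dilution and noise

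*Protocol*

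**What the plan says.** The population in Protocol section 3.4 is "Female aged 15-49 years with Metabolic Syndrome in Wakiso district", the range that the operational definitions use for reproductive age ("This refers to the female in the age group 15-49 years"). The exclusions are "Females with chronic diseases such as liver, kidney, heart diseases or any diseases that could be worsened or affected by intervention sessions", and then "participants on a prescribed diet plan, and those with the potential to undergo any surgical procedure during the intervention period". Pregnancy is not listed.

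Participants come from an earlier survey (section 3.5): "We will use the database of a baseline study conducted to determine the prevalence of Metabolic Syndrome in Wakiso district". That survey's own eligibility rules are not given.

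The primary outcome (section 3.6) is the between-group "change in MetS prevalence after 3 months from start of intervention". MetS requires at least three of five factors: waist of 80 cm or more, low HDL, raised triglycerides, raised blood pressure and raised fasting glucose. Weight, waist and BMI are secondary outcomes. Section 3.9 lists a medical history among the baseline items but names no pregnancy question or test, at baseline or endline. The Data Analysis section drops participants who attend under 60% of the intervention sessions. Pregnancy appears only in the Background, which links MetS to hypertension and diabetes of pregnancy.

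**The concern.** Pregnancy is not a disease, so the wording on diseases affected by the sessions does not clearly cover it. Followed as written, the plan admits pregnant women and leaves no record of who they were.

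Gestation or delivery can change waist, weight and BMI over three months in either arm, for reasons unrelated to the programme. A woman may meet the waist criterion at entry partly because she is pregnant, and her status at endline may reflect pregnancy or a recent delivery. The outcomes of such women say little about the intervention.

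This cannot be left to a statistical analysis plan. Eligibility and the data items collected are protocol matters, and an analysis cannot account for a status that was never recorded.

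**Working it through.** **Inputs from the Protocol.** Section 3.7 gives 5% significance, 80% power, a difference of 0.20 in MetS prevalence, and totals of 98, then 104 after the design effect, then 120 after 10% for dropout and non-consent. Allocation is 1:1.

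**Assumptions.** The Protocol gives neither the two arm rates nor a pregnancy rate. I take endline MetS rates of 95% (control) and 75% (intervention), a two-sided test, and a pregnant share *q* of 2%, 5% or 10%.

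**The plan's figure.** With 0.95 and 0.75 the pooled rate is 0.85, and n per arm = [1.96·√(2·0.85·0.15) + 0.8416·√(0.95·0.05 + 0.75·0.25)]² / 0.20² = (1.96·0.5050 + 0.8416·0.4848)² / 0.04 = 48.8. This rounds up to 49, or 98 in total, and matches. The match does not prove that these rates were used, because 0.90 vs 0.70 one-sided also gives 98. After a 10% loss, 120·0.9 = 108, or 54 per arm.

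**1. How likely is any pregnancy?** Expected number = 120·*q*; chance of at least one = 1 − (1 − *q*)^120.

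| *q* | Expected number | Chance of at least one |
|---|---|---|
| 2% | 2.4 | 91% |
| 5% | 6 | over 99% |
| 10% | 12 | over 99% |

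**2. Dilution.** Suppose every pregnant woman is MetS-positive at endline in either arm. Each arm's rate becomes (1 − *q*)·p + *q*, and the difference becomes 0.20·(1 − *q*). Power = Φ[(difference − 1.96·SE0)/SE1], where SE0 uses the pooled rate and SE1 the separate rates, with 54 per arm.

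| *q* | Control | Intervention | Difference | Power |
|---|---|---|---|---|
| 0 | 95.0% | 75.0% | 20.0 points | 84% |
| 5% | 95.25% | 76.25% | 19.0 points | 82% |
| 10% | 95.5% | 77.5% | 18.0 points | 79% |

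For *q* = 0, SE0 = √(2·0.85·0.15/54) = 0.0687 and SE1 = √(0.235/54) = 0.0660, so Φ[(0.20 − 0.1347)/0.0660] = Φ(0.99) = 84%. At 90% vs 70% the same steps give 74.5%, 71.7% and 68.7%. The starting level depends on the assumed rates, but the loss is similar.

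**3. Uneven split by chance.** Under the same assumption, each extra pregnant woman in the intervention arm raises its expected rate by (1 − 0.75)/60. Three to four such women give 1.25 to 1.7 points. In the control arm the step is (1 − 0.95)/60, so three to four give 0.25 to 0.33 points. With 60 per arm, an excess of three or more in one arm has a probability of about 21% with 6 pregnant women and 36% with 12.

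**4. The attendance rule.** Only the intervention arm has sessions to attend. In the extreme case where every pregnant woman falls below 60% attendance, the intervention rate returns to 75% while the control rate stays at 95.25% or 95.5%. The difference is then 20.25 or 20.5 points, against 19 or 18 if all are kept. That is a shift of 1.25 or 2.5 points in favour of the intervention.

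**The case against.** The strongest case on the other side is that the problem may be small or already handled. The source survey may have left out pregnant women. Candidates are screened before invitation (section 3.7, Sample selection), and a medical history is taken at baseline. Randomisation balances pregnancy in expectation. MetS needs three of five factors, so waist alone neither creates nor sustains the diagnosis.

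Much of this stands. It limits the size of the effect and rules out a claim of systematic bias from pregnancy at entry. It does not close the gap: the survey's criteria are not shown, a survey exclusion would not cover later conception, and no rule uses the screening or the history to identify pregnancy.

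Three stronger readings are tempting but unsupported:

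- **That outcomes will certainly be affected.** The Protocol gives no pregnancy rate, so likely is as far as one can go.
- **That three or four unevenly split women shift the result by 5 to 7 points (3/60 to 4/60).** This needs each of them to have the opposite outcome from the one she would otherwise have had. If they simply stay MetS-positive, most would have been positive anyway, and the shift is at most 1 to 2 points. Delivery before endline could push the other way by appearing as remission, but nothing in the documents allows that to be sized.
- **That the weight-loss content of the sessions ("goals for weight loss, techniques for diet compliance for weight loss") adds to the statistical case.** It raises a question of clinical suitability, which is not evidence of outcome error and is not argued here.

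**Conclusion.** The gap is real and its expected effect is modest. Section 3.4 admits pregnant women and no section records pregnancy, so misclassified outcomes, a diluted effect and added noise in waist, weight and BMI are likely. At assumed pregnant shares of 5-10% and rates of 95% vs 75%, the power loss is about 2 to 5 percentage points.

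These figures rest on pregnancy shares, arm rates and a no-remission assumption that the Protocol does not supply. The absence of any rule or data item for pregnancy does not depend on them. The one route to a difference between arms is the 60% attendance rule, which can act on the intervention arm only. The change is worth making because it costs little and the missing status cannot be recovered afterwards.

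**What to change.** - **Eligibility.** Add pregnant at enrolment to the exclusions in section 3.4.
- **Timing.** Ask at the screening step in section 3.7, before names are allocated. This order must be written down: the allocation concealment text randomises survey names before consent, and section 3.9 takes the medical history only at baseline data collection. If screening cannot come first, pregnancy should be ascertained at baseline by staff blind to allocation, so that exclusions cannot depend on arm.
- **Follow-up.** Record pregnancy or delivery at endline in both arms.
- **Analysis.** Keep women who conceive after enrolment in their randomised arm for the primary analysis, whatever their attendance. Add one supportive analysis without them, labelled as such because it excludes women on an event after randomisation.

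The cost is one criterion, one question per visit and a stated order of screening and allocation. A few women become ineligible, and the conclusions apply to women not pregnant at entry.
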